## **4.0 PRETREATMENT EVALUATION**

Pre-enrollment screening tests and evaluations will be used to determine the eligibility of each candidate for study inclusion. All enrollment evaluations must be assessed within the interval specified prior to treatment. All dates are specified below but may occur on the following day if it falls on a weekend or holiday.

### **4.1 CLINICAL: (within 6 weeks prior to registration)**

- 4.1.1Complete history and physical examination.
- 4.1.2Height, weight, and ECOG Performance Status.
- 4.1.3Baseline evaluation of symptoms and medications. Patients medication list will be reviewed and compared to the list in Appendix F. Medication adjustment will be performed to eliminate the possibility of interaction with Sunitinib.

### **4.2 LABORATORY: (within 6 weeks prior to registration)**

- 4.2.1Hematology: Complete blood count, differential and platelet count.

## [name], Phase II Study of BCG followed by Sunitinib for High risk NMIBC

4.2.2 Comprehensive panel: sodium, potassium, chloride, bicarbonate, BUN, creatinine, glucose, calcium, AST, ALT, alkaline phosphatase, bilirubin, total protein and albumin.

4.2.3 TSH

4.2.4 Urine cytology

### 4.3 IMAGING AND DIAGNOSTIC STUDIES: (within 6 months prior to registration)

4.3.1 Computed tomography scan (with contrast), intravenous pyelogram, or magnetic resonance imaging of the abdomen and pelvis.

4.3.2 A non-contrasted CT combined with renal/bladder ultrasound can be obtained for those patients with a contra-indication to CT and/or MRI

### 4.4 ELECTROCARDIOGRAM. (within 3 months of registration)

### 4.5 MUGA SCAN (within 6 weeks of study enrollment)

## 5.0 REGISTRATION PROCEDURES

### 5.1 GENERAL GUIDELINES

Eligible patients will be recruited from the University of Michigan, Department of Urology Clinics. Patients signing informed consent and meeting eligibility criteria will be registered on study by the Study Coordinator. Once registration is complete, the registrar will provide the registering individual a study subject identification number.

Following registration, patients should begin protocol treatment within 3 weeks. Issues that would cause treatment delays should be discussed with the Principal Investigator.

## 6.0 TREATMENT PLAN (Treatment must begin within 6 weeks after registration)

### 6.1 BCG

#### 6.1.1 DOSE LEVELS: Dose Levels for TICE BCG

Dose Levels for TICE BCG

Dose Level	Weekly Dose/ Route	Dispensed As	Schedule
Starting dose level: 0	50 mg reconstituted in 50 ml normal saline/intravesical	vial	1day/week x 6 weeks

-1	25 mg reconstituted in 50 ml normal saline/intravesical	½ vial	1day/week x 6 weeks
-2	12.5 mg reconstituted in 50 ml normal saline/intravesical	¼ vial	1day/week x 6 weeks

#### *6.1.2 BCG ADMINISTRATION*

- Patients will undergo urinalysis in clinic and the decision to proceed with BCG therapy will be based on standard clinic procedures (Appendix B).
- BCG is delivered via a 12-16 French Red Robinson catheter by a clinical nurse. Patients are encouraged to decrease fluid intake for up to 6 hours prior to administration. BCG is retained in the urinary bladder for two hours following administration. Patients are requested to void sitting down to avoid contamination and requested to disinfect the toilet with bleach after as well as for any voids up to 6 hours after treatment.
- Study drug TICE BCG will be administered by a nurse in clinic as 50 mg reconstituted in 50 ml sterile normal saline 1 time/week for a total of 6 weeks. Patients without a complete response after the initial cycle will be offered a second identical cycle.
- The Study drug dose may be adjusted according to individual patient tolerance as outlined below in section 10. The BCG can be diluted in ½ to ¼ the original dose.
- Induction and/or maintenance BCG may be administered by a local urologist at the approval of the principal investigator
  - Induction BCG protocol by local urologist will be verified by the principal investigator to ensure compliance with study protocol
  - Maintenance BCG will be administered following the study calendar.
    - Deviations to the maintenance BCG schedule will be reported to the study coordinator along with reason. Ultimately, the administration of maintenance BCG and its timing are at the discretion of the treating physician.
    - Records will be obtained from the local urologist to document dose, dates of administration and completion of course for a length of 2 years following completion of induction course of BCG.

#### *6.1.3 CONCOMITANT MEDICATION(S)*

Intravesical BCG is not metabolized. Because BCG works by stimulating the immune system, patients on immunosuppressive agents (corticosteroids) or immunocompromised (HIV infection, transplant patients on immunosuppressive regimens) should not be given BCG. In addition, antimicrobial therapy should be avoided during BCG administration due to the potential antimicrobial effect on the BCG itself. **(PLEASE REFER TO CONCOMINANT MEDICATION SECTION IN REGARD TO SUNITINIB)**

#### *6.1.4 DOSE REDUCTIONS: Please refer to Section 11.*

### 6.1.5 SUPPORTIVE CARE GUIDELINES:

- Irritative bladder symptoms occur in 50% of patients
  - For patients with bothersome symptoms, medications such as pyridium, propantheline bromide, oxybutynin and acetaminophen can be used
- “Flu-like” symptoms (malaise, fever, chills)
  - Are related to the immune and hypersensitivity response and can be managed with ibuprofen, acetaminophen, and antihistamines
- Ocular symptoms (uveitis, conjunctivitis, iritis, keratitis, granulomatous choreoretinitis) alone or in combination with joint symptoms (arthritis, arthralgia), urinary symptoms, and/or skin rash have been reported. Patients positive for HLA-B27 appear to be at elevated risk
  - Dose reduction will be attempted
  - If persistent, BCG will be halted although patients will be allowed to continue to the Sunitinib portion of the study.
- Infection: Urinary tract infection, prostatitis, orchitis/epididymitis have all rarely been reported with BCG. Serious disseminated infections to the lung, liver, bone, bone marrow, kidney, and regional lymph nodes have been reported in case reports in the literature. Finally, sepsis has been reported with associated mortality.
- If a patient develops persistent fever ( $> 38.5$  C) or experiences an acute febrile illness consistent with BCG infection, BCG will be immediately discontinued and the patient will be evaluated for BCG infection
- Local infections may often be managed with discontinuation combined with a fluoroquinolone antibiotic such as ciprofloxacin or levofloxacin. However, rare cases of epididymitis and orchitis have not been successfully managed and may require antituberculosis therapy and/or orchiectomy
- More serious infections will be evaluated and might require one of the following actions:
  - Hospital admission with urine and blood cultures
  - Supportive therapy
  - Infectious disease physician consultation
  - Initiation of anti-tuberculosis therapy including isoniazid, rifampin, and/or ethambutol (not pyrazinamide)

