## 10.0 DOSING DELAYS/DOSE MODIFICATIONS

## 10.1 TICE BCG

### 10.1.1 DELAYS

- For patients experiencing bladder related symptoms, all attempts will be used to supportive care to have the patient complete a complete 6 week course at the full dose.
- Patients with gross hematuria and/or evidence of urinary tract infection during treatment as documented by urinalysis and/or confirmed by urine culture will be delayed administration of the dose by 1 week and restarted after confirming absence of gross hematuria and/or lack of nitrite positivity on dipstick urinalysis.
- Those patients with a greater than 3 week delay between doses during the 1st induction course will be removed from the study prior to initiation of sunitinib and be replaced with another eligible patient. Those unable to complete a 2nd induction course of BCG will be offered alternative therapy and followed for secondary endpoints where applicable.
  - Any patient with systemic infection caused by TICE BCG will be withdrawn from further BCG treatment. If this occurs during the first induction course, these subjects will be replaced, otherwise, patients will be offered alternative therapy and followed for applicable secondary endpoints.
  - Patients on maintenance BCG therapy will be given the full dose unless persistent urinary symptoms or systemic side effects (malaise, fever, fatigue) deter treatment. Dose reduction to -1 will be attempted first. Patients will be allowed to decrease dose to -2 if intolerance persists. Those patients who do not tolerate a dose of -2 during (see table in section 6.1) maintenance therapy will be withdrawn from further BCG administration and offered alternative treatment plan at the discretion of the treating clinician.

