### 10.1.2 REDUCTION

- Intrapatient dose reduction by 1, and if needed 2- dose level(s) will be allowed (see Table below) depending on the type and severity of toxicity encountered provided that criteria for patient withdrawal from study treatment have not been met.
- All intra-patient dose reductions are relative to the lowest dose level of the current cycle.
- No more than 2 dose reductions are permitted in any patient. If further dose reduction is required, the patient must be removed from further BCG administration.
- The dosing period may be extended for BCG as outlined in section above
- The below table describes the recommended dose modifications for study treatment associated toxicity.

TABLE: DOSE MODIFICATION FOR BCG BASED ON TOXICITY AND GRADE

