# if BCG infection of grade 3 or 4 occurs during the 1st induction course, patients will be withdrawn from the study and replaced. Otherwise, patients will be offered alternative therapy at the discretion of the treating clinician and followed for appropriate endpoints.

### 10.2 SUNITINIB: In the event of any (CTC version 3) drug related grade 3 or 4 non-hematologic or

Toxicity	Grade 1	Grade 2	Grade 3	Grade 4
Irritative Bladder symptoms	Continue at the same dose level	Continue at the same dose level.	Dose reduction to -1. If Grade 3 toxicity persists, reduction to -2. Discontinuation will occur at the discretion of the treating clinician.	Dose reduction to -1. If Grade 4 toxicity persists, reduction to -2. Discontinuation will occur at the discretion of the treating clinician.
Fever, chills and "flu-like" symptoms	Continue at same dose level.	Continue at same dose level.	Dose reduction to -1. If Grade 3 toxicity persists, reduction to -2. Discontinuation will occur at the discretion of the treating clinician	Dose reduction to -1. If Grade 4 toxicity persists, reduction to -2. Discontinuation will occur at the discretion of the treating clinician
Occular symptoms +/- joint symptoms	Continue at the same dose level.	Continue at the same dose level.	Dose reduction to -1. If Grade 3 toxicity persists, reduction to -2. Discontinuation will occur at the discretion of the treating clinician	Dose reduction to -1. If Grade 4 toxicity persists, reduction to -2. Discontinuation will occur at the discretion of the treating clinician
Infection	Treat* and continue at same dose after resolution of symptoms within 2 weeks	Treat* and continue at same dose after resolution of infection within 2 weeks	Withdraw BCG treatment#	Withdraw BCG treatment#

grade 4 hematologic adverse event(s) drug should be held until the toxicity resolves to < grade 1 and then the drug should be restarted at -1 dose level (see 6.1).

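### The BCG dosing rules for fever leave out the stop-and-evaluate exception that Section 6.1.5 makes mandatory

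*Combined protocol and SAP*

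**What the plan says.** Section 6.1.5 separates two kinds of fever during BCG treatment. Ordinary flu-like symptoms, fever included, "Are related to the immune and hypersensitivity response and can be managed with ibuprofen, acetaminophen, and antihistamines". Persistent fever above 38.5 C is a trigger for stopping. So is a second situation, in which the patient "experiences an acute febrile illness consistent with BCG infection, BCG will be immediately discontinued and the patient will be evaluated for BCG infection". The rule has no limit by toxicity grade or by treatment phase.

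The dose for a patient with fever is set in two other places.

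- **BCG dose-modification table, Section 10.1.2, row for fever, chills and flu-like symptoms.** Grades 1 and 2: "Continue at same dose level". Grade 4: "Dose reduction to -1. If Grade 4 toxicity persists, reduction to -2. Discontinuation will occur at the discretion of the treating clinician". Grade 3 is worded in parallel.
- **Section 10.1.1, maintenance.** "Patients on maintenance BCG therapy will be given the full dose unless persistent urinary symptoms or systemic side effects (malaise, fever, fatigue) deter treatment". Then: "Dose reduction to -1 will be attempted first. Patients will be allowed to decrease dose to -2 if intolerance persists".

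Neither place mentions the 38.5 C threshold, evaluation for BCG infection, or Section 6.1.5.

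**The concern.** BCG is a live organism, and Appendix B spaces instillations 7 days apart. Confirmed systemic BCG infection and grade 3 or 4 infection already lead to withdrawal. The exposure is therefore the interval before infection is confirmed or excluded. In that interval Section 6.1.5 says stop and evaluate, whereas the fever row and the maintenance sentence say continue or reduce. Persistence in particular points in opposite directions: it triggers a stop in 6.1.5 and a further reduced dose in the other two places.

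The layout makes this more likely to matter. Section 6.1.2 sends the reader to Section 10 for dose adjustment, and 6.1.4 points to Section 11, which is pharmaceutical information. Section 6.1.2 also allows a local urologist to give induction or maintenance BCG and leaves maintenance to the treating physician. A clinician who looks up fever in Section 10 would not meet the stop rule.

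**Working it through.** There is no stated design figure to reproduce. The check sets the instructions side by side and then sizes the issue from the protocol's own side-effect frequencies.

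**1. What each instruction does with a persistent fever above 38.5 C**

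| Place | Action | Mandatory stop? |
|---|---|---|
| 6.1.5 | Stop BCG, evaluate for infection | Yes |
| Fever row, grades 1 and 2 | Same dose | No |
| Fever row, grades 3 and 4 | Reduce to -1, then -2 if it persists; stopping is the clinician's choice | No |
| 10.1.1, maintenance | Reduce to -1, then -2; withdraw only if -2 is not tolerated | No |

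The documents do not give the CTCAE version 3 temperature cut-offs, so the grade of such a fever cannot be stated. The result does not depend on it, because no grade in the row makes stopping mandatory.

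**2. Whether another provision closes the gap**

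- The Infection row and the systemic-infection bullet in 10.1.1 are framed around infection. Neither clearly covers a fever still under evaluation, and the fever row does not point to them.
- Section 10.1.2 allows dose reduction only when withdrawal criteria are not met. That limits reductions, not the grade 1 and 2 instruction to continue. The removal criteria in Section 8.1 do not list persistent fever.
- The delay rule in 10.1.1 covers gross hematuria and urinary tract infection, not fever.
- Appendix B takes a temperature before each instillation but sets no value at which the dose is withheld. It asks patients to call above 101.5. No unit is printed; if Fahrenheit, this is (101.5 − 32) × 5/9 = 38.6 C, close to the 6.1.5 threshold, but it prompts a call and not a stop.

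**3. How often these instructions would be used**

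Section 11.1 lists fever above 38 C in 10–50% of BCG patients and systemic infection in fewer than 1%. At least 36 patients start BCG if both stages accrue (Section 16.1).

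- Fever above 38 C: 0.10 × 36 = 3.6 to 0.50 × 36 = 18 patients.
- Systemic infection: fewer than 0.01 × 36 = 0.36 patients.

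The first figure covers any fever above 38 C, which is wider than the 6.1.5 trigger.

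**4. Why both places need the change**

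Assume one instillation per week of each 3-week maintenance course, and a patient who responds to the first cycle after 6 induction instillations.

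- Calendar 2 shows courses at months 3, 6, 12, 18 and 24: 5 × 3 = 15, and 15/(6 + 15) = 71% of instillations.
- The Protocol Summary gives a course every 6 months for 2 years: 4 × 3 = 12, and 12/(6 + 12) = 67%.

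Correcting the table alone would leave the maintenance sentence, which covers most scheduled instillations, unchanged. These shares count instillations and do not measure risk.

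**The case against.** The strongest reply is that the rule already exists and is mandatory, so only a cross-reference is missing. Section 10.1.2 presents its table as advice: "The below table describes the recommended dose modifications for study treatment associated toxicity". The stop rule in 6.1.5 sits among the infection bullets, and the table mirrors that split with separate fever and infection rows. A careful reader would take the fever row to mean the expected immune reaction and send suspicious fever down the infection path. The Infection row does not say that infection must first be confirmed. The maintenance sentence concerns tolerability, and the bullet just before it says: "Any patient with systemic infection caused by TICE BCG will be withdrawn from further BCG treatment". Physicians keep discretion throughout, and the principal investigator verifies induction given locally.

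Much of this stands. Section 6.1.5 probably prevails, the two texts can be reconciled, and the harm guarded against is rare. These points lower the severity. They do not remove the omission. The grade 1 and 2 cells say continue without qualification, the withdrawal proviso does not reach them, and no dosing provision clearly covers fever while infection is being excluded. Discretion to stop is also weaker than a requirement to stop.

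**Conclusion.** The concern holds. A stated dosing rule, followed as written, gives further BCG at the same or a reduced dose where Section 6.1.5 requires it to be stopped. This is a missing exception in two places and should be fixed on safety grounds.

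The fever instructions would be used often (about 4 to 18 of 36 patients with fever above 38 C), while the event guarded against is rare (fewer than 0.4 of 36). The number who would meet the 6.1.5 trigger cannot be derived from the documents. The counts assume that the Section 11.1 frequencies apply to this population and that both stages accrue. Sample size, power and error rates are unaffected.

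**What to change.** Add one sentence to every grade of the BCG fever row in Section 10.1.2 and to the maintenance text in Section 10.1.1, for example:

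*Exception, at any grade: for persistent fever above 38.5 C, or a febrile illness suggesting BCG infection, stop BCG and evaluate as 6.1.5 requires; give no further dose, full or reduced, while evaluation is pending.*

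Leave 6.1.5 as written. Leave to the medical team whether and when BCG may restart once infection is excluded. Keep the removal and replacement rules unchanged.

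The cost is one sentence in two places, with no new procedure and no stop beyond what 6.1.5 already demands. Some patients whose fever proves non-infectious will have a dose delayed. In the first induction course, a gap of more than 3 weeks between doses would trigger the existing rule in 10.1.1 for removal and replacement.

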## 6.2 SUNITINIB (Treatment with Sunitinib will occur according to the study calendar)

### 6.2.1 DOSE LEVELS: Dose Levels for Sunitinib

Dose Level	Daily Dose/ Route	Dispensed As	Schedule
Starting dose level: 0	50 mg, PO	1 x 50-mg capsules	4 weeks on and 2 weeks off, Q 6 weeks

[name], Phase II Study of BCG followed by Sunitinib for High risk NMIBC

-1	37.5 mg, PO	1 x 25 mg capsule and 1x 12.5 mg capsule	4 weeks on and 2 weeks off, Q 6 weeks
-2	25 mg, PO	1 x 25-mg capsules	4 weeks on and 2 weeks off, Q 6 weeks

#### **6.2.2 SUNITINIB ADMINISTRATION**

- Study drug (Sunitinib) will be given at 50 mg/day as a single agent for 4 consecutive weeks followed by a 2-week rest period to form a complete cycle of 6 weeks. Study drug will be orally self administered once daily without regard to meals.
- The Study drug dose may be adjusted according to individual patient tolerance as outlined below in section 10.
- Patients must be provided with a diary to document compliance, (Appendix C).
- Patients will be required to return all bottles of study medication at the beginning of each cycle. The number of capsules remaining will be documented and recorded.

#### **6.2.3 CONCOMITANT MEDICATION(S)**

Sunitinib is metabolized primarily by liver enzymes, in particular CYP3A4. Caution is recommended when administering study drug with inhibitors or inducers of the CYP3A4 family (see appendix G).

#### **6.2.4 DOSE REDUCTIONS: Please refer to Section 11.**

#### **6.2.5 SUPPORTIVE CARE GUIDELINES:**

- Diarrhea
  - Lomotil or Imodium may be used by patients developing diarrhea during treatment.
- Hypertension
  - Blood pressure should be well controlled before starting study drug.
  - Standard blood pressure medications should be used for patients that develop hypertension during treatment.
  - Diltiazem and verapamil should be avoided if possible as they are potential inhibitors of the CYP3A4 pathway (see section 6.2.3).
  - If hypertension develops or worsens while on study drug, treatment should first be with optimizing standard anti-hypertensive agents. If refractory, study drug dose modifications can be made.
  - In cases of severe hypertension (>200 mmHg systolic or 110 mmHg diastolic) temporary suspension of study drug is recommended until hypertension is controlled.
- Fatigue
  - For intolerable fatigue, the next cycle of treatment may be delayed by one week.

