### 7.2 SUNITINIB

- Patients will receive a single 6 week cycle of sunitinib 2 weeks following a 6 week course of intravesical BCG. Complete responders as determined by no cancer on endoscopic biopsy

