**Management of cardiac ejection fraction.**

Toxicity	Grade 1	Grade 2	Grade 3	Grade 4
Non-hematologic	Continue at the same dose level	Continue at the same dose level.	Withhold dose until toxicity is grade $\leq 1$ , or has returned to baseline, then resume treatment at the same dose level or reduce the dose by 1 level at the discretion of the investigator*.	Withhold dose until toxicity is grade $\leq 1$ , or has returned to baseline, then reduce the dose by 1 level and resume treatment, or discontinue at the discretion of the investigator*.
cardiac toxicity:	Continue at the same dose level.	Continue at the same dose level except in the event of Non-urgent ventricular paroxysmal dysrhythmia requiring intervention, Withhold dose until toxicity is grade $\leq 1$ , then reduce dose by 1 level and resume treatment.	Remove from further therapy, follow for applicable endpoints	Remove from further therapy, follow for applicable endpoints
Neurotoxicity	Continue at the same dose level.	Withhold dose until toxicity is grade $\leq 1$ , then continue at same dose level.	Withhold dose until toxicity is grade $\leq 1$ , then reduce the dose by 1 level and resume treatment.	Remove from further therapy, follow for applicable endpoints
Fever, chills and "flu-like" symptoms	Continue at same dose level.	Continue at same dose level.	Withhold dose until toxicity is grade $\leq 2$ , or has returned to baseline, then resume treatment at the same dose level.	Withhold dose until toxicity is grade $\leq 2$ , then reduce the dose by 1 level and resume treatment.
Hematologic	Continue at the same dose level.	Continue at the same dose level.	Withhold dose until toxicity is grade $\leq 2$ , or has returned to baseline, then resume treatment at the same dose***.	Withhold dose until toxicity is grade $\leq 2$ , then reduce the dose by 1 level and resume treatment***.

All patients will undergo a MUGA scan prior to enrollment in the study. Patients proceeding to a second cycle of therapy (BCG followed by sunitinib) will undergo a MUGA scan prior to initiation of the second cycle. Patients with an ejection fraction lower than the institutional lower limit of normal will not receive further study treatment per protocol and will be offered alternative therapy as directed by the treating clinician.

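### Section 6.2.5's sunitinib instructions for hypertension and fatigue do not match sections 10.2 and 10.2.1, and nothing says that section 10 overrides it

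*Combined protocol and SAP*

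**What the plan says.** **Section 6.2.5, hypertension.** New or worsening hypertension is to be met first with better blood-pressure medication. After that, "If refractory, study drug dose modifications can be made". For high readings, "In cases of severe hypertension (>200 mmHg systolic or 110 mmHg diastolic) temporary suspension of study drug is recommended until hypertension is controlled". No toxicity grade, restart dose level or time limit is given.

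**Section 6.2.5, fatigue.** "For intolerable fatigue, the next cycle of treatment may be delayed by one week". This is the only action on study drug that 6.2.5 names for fatigue.

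**Section 10.2.** The scope is broad: "In the event of any (CTC version 3) drug related grade 3 or 4 non-hematologic or" grade 4 hematologic events. The instruction is that "drug should be held until the toxicity resolves to < grade 1 and then the drug should be restarted at -1 dose level".

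**Section 10.2.1 and its table.** For grade 3 non-hematologic toxicity, drug is withheld until grade 1 or lower or baseline, "then resume treatment at the same dose level or reduce the dose by 1 level at the discretion of the investigator". After grade 4 the investigator either resumes one level lower or discontinues. Grades 1 and 2 continue unchanged. Recovery must come within 4 weeks. A separate cardiac row says, for grades 3 and 4, "Remove from further therapy, follow for applicable endpoints". The table does not say whether hypertension belongs in that row.

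**Section 7.2.** "Patients will receive a single 6 week cycle of sunitinib". Complete responders then go to maintenance BCG. Only patients with residual disease who take a second course receive sunitinib again.

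**Cross-references.** Section 6.2.2 sends dose adjustment to section 10. Section 6.2.4, directly above 6.2.5, sends dose reductions to section 11, which is pharmaceutical information.

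**The concern.** A prescriber facing drug-related hypertension or severe fatigue finds two sets of instructions in one protocol. They differ in what starts a hold, what ends it, and at what dose treatment resumes. Section 11.2 lists fatigue in at least half of patients and hypertension in 10-50%, and section 2.4 names fatigue as the main dose-limiting toxicity in phase 1. These are therefore toxicities for which the text will be consulted.

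Three things are at stake: consistent safety handling, sunitinib exposure before the week 14 biopsy, and a clear standard for the protocol deviations to be reported under section 17.3.1. An action that follows one section can depart from the other.

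**Working it through.** No statistical figure in the plan bears on this point. The check is a comparison of text plus a count of weeks and patients.

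**Step 1. Hypertension.** The documents do not map the mmHg figures to CTCAE version 3 grades, so every combination has to be considered. The event is assumed to be drug-related and handled as non-hematologic.

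| Event | Section 6.2.5 | Sections 10.2 / 10.2.1 |
|---|---|---|
| Grade 3-4, not above the mmHg figures | Blood-pressure medication first; dose change optional if refractory | Hold drug |
| Grade 3-4, above the mmHg figures | Suspension recommended until *controlled*; no restart level or time limit | Text: hold to below grade 1, restart at -1. Table: hold to grade 1 or lower or baseline; same level or one lower after grade 3, one lower or discontinue after grade 4. Recovery within 4 weeks |
| Grade 1-2, above the mmHg figures | Suspension recommended | Continue at same dose |
| Grade 1-2, not above the mmHg figures | Blood-pressure medication first; dose change optional if refractory | Continue at same dose |

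Any grade 3-4 event falls in row 1 or row 2. In row 1 the sections differ on whether to hold at all. In row 2 they state different ends to the hold, and only section 10 gives a restart level and a time limit. Some mismatch therefore exists whatever grades the mmHg figures correspond to. If hypertension were placed in the cardiac row, grade 3 or 4 would mean removal from further therapy, which 6.2.5 does not match either.

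**Step 2. Is 6.2.5 a recognised exception?** Section 10.2.1 lists exemptions: certain lipase, amylase, uric acid and phosphate abnormalities, and certain lymphopenia and anemia. Neither hypertension nor fatigue is among them.

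**Step 3. Fatigue and the next cycle.** Inputs are from section 7.2, the section 13 calendar, section 2.4 and the design rates in section 16.1.

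- Sunitinib cycle 1 runs over weeks 8-12, with the biopsy at week 14. A second course repeats weeks 1-14, so sunitinib resumes at about week 14 + 8 = 22 at the earliest. That is 22 - 12 = 10 weeks after the last cycle 1 dose.
- Section 2.4 puts dose-limiting fatigue at days 10-15. From week 8 this is week 8 + 10/7 = 9.4 to 8 + 15/7 = 10.1, close to the week 10 visit and inside cycle 1.
- 3-month complete responders at the design rates: 36 x 0.55 = 19.8 and 36 x 0.75 = 27, so about 20 to 27 of 36. They have no later sunitinib cycle.
- The remainder, 36 - 27 = 9 to 36 - 20 = 16, is the most that could start a second course. Some of these may progress or choose other treatment. For those who do start, the course opens with BCG.

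**Step 4. Effect on the design.** Under section 16.1 a patient is evaluable after one dose of sunitinib. Holds and dose reductions therefore do not change the counts of 24 and 36 or the response cut-offs.

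**The case against.** The strongest reply is that the sections complement each other. Section 6.2.5 is supportive-care guidance, section 6.2.2 names section 10 as the place for dose adjustment, and the pointer to section 11 in 6.2.4 looks like a misnumbering. Where 6.2.5 is silent on restart level and recovery time, section 10 can fill the gap. The line on refractory hypertension may itself point to section 10. Much of this stands, and it narrows the point. It does not settle row 1 above, where one section holds drug and the other treats blood pressure first. Nor does any text say that section 10 prevails.

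A reader might infer more than the documents support:

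- **That 6.2.5 leaves no action for fatigue in the current cycle.** It does not. The fatigue line is permissive, section 10 still covers grade 3-4 fatigue, and section 11.2 lets the investigator suspend or reduce for safety.
- **That the next cycle never exists.** It exists for patients with residual disease who take a second course.
- **That 6.2.5 is weaker because it only recommends.** The 10.2.1 table is also introduced as recommended.
- **That sites will diverge.** Section 5.1 recruits from one institution, the local-urologist provision in 6.1.2 covers BCG only, and a medical oncologist prescribes sunitinib. The risk lies between prescribers.
- **That 18 or more of 36 patients are affected.** Applied to 36 patients, section 11.2 gives at least 36 x 0.50 = 18 with fatigue and 36 x 0.10 = 3.6 to 18 with hypertension. These are all-grade frequencies, and grade 1-2 non-hematologic events continue unchanged under the table.

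It is also fair that part of the restart uncertainty comes from 10.2 disagreeing with its own table. Settling that alone would still leave 6.2.5 unmatched.

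**Conclusion.** The point holds as a minor-to-moderate internal inconsistency in the safety instructions. It is not a criticism of the design. For drug-related hypertension, 6.2.5 and section 10 do not match on the trigger or on the end of a hold, and only section 10 states a restart level and a recovery limit. For fatigue, the one drug action in 6.2.5 has no application to 3-month complete responders and does not address fatigue within cycle 1.

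The number of patients affected cannot be derived, because the documents tie neither the mmHg figures nor *intolerable* to a grade. Sunitinib exposure before week 14 and the toxicity summaries could vary with the section followed, but an effect on the 3-month complete response rate is not shown. The conclusion assumes that hypertension and fatigue count as non-hematologic events under section 10. No view is taken on which clinical rule is right.

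**What to change.** - Reconcile 6.2.5 with 10.2 and 10.2.1 so that, for hypertension and for fatigue, the protocol states one trigger, one recovery criterion and one restart rule. State whether hypertension belongs in the non-hematologic or the cardiac row. The clinical team must choose the content.
- Say which section governs if both apply.
- Correct the pointer in 6.2.4 from section 11 to section 10. In the same edit, correct the references in 10.2 and 10.2.1 to 6.1 for dose levels: that section holds the BCG table, and the sunitinib levels are in 6.2.1.
- Reword the next-cycle line to fit one sunitinib cycle per course.

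The cost is a few lines of wording and cross-references in a protocol amendment. Sample size, endpoints and analyses do not change.
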